## **Recruitment & Retention Pilot Outcomes**

### Meeting Eligibility Criteria.

The primary outcome is the percentage of subjects who meet final eligibility criteria (i.e., enrollment). We chose this as the outcome based on our data suggesting that subjects who meet these criteria are highly likely to reach ITT status.

### Impressions of Research.

Attitudes towards research; motivations for participation; perceived risks/benefits of research; personal financial wellbeing and perceptions of influence or coercion will be assessed via text survey at baseline (following phone screen), mid-way through participation and at study completion. Study staff will attempt to contact subjects who withdraw or are lost-to-follow up to identify reasons for withdrawal. We will assess overall satisfaction with the study, acceptability of the frequency and content of messages (IP and IC groups only). For all models, a term will be included for individual study as well as other relevant covariates (e.g., sex, age, income).

**Table 1. Study Time Points and Measures**

Study Week	0	1	2	3	4	5	6	7	8	12		
Session	Phone Screen	Intake	L1	L2	PQ	TQD	C1	C2	C3	C4	EOT	Post- Study
TREATMENT												
TN							X	X	X	X	X	
Counseling d						X	X	X	X	X		
SCREENING/COVARIATES												
Demographics/Smoking Hx/FTND d		X										
Urine Drug Screen		X	X	X								
Urine Pregnancy Screen		X	X	X								
Blood Pressure		X	X	X								
Shipley IQ d		X										
Medical History d		X										
Concomitant Medication Review d		X	X	X	X	X	X	X	X	X	X	
Adherence to Anti-retrovirals* d			X	X	X	X	X	X	X	X	X	
Nicotine Metabolite Ratio (urine and plasma)		X										
Neuroinflammation		X										
Viral Load Assessment*		X										X a
HIV Lab Assessment/HIV Blood Test*		X										
Debriefing Phone Call												X
PSYCHOLOGICAL AND SUBJECTIVE MEASURES												
Psychiatric Hx (MINI) d		X										
Suicidality (C-SSRS) d		X										
Bipolar Disorder Symptoms (MADRS, YMRS, additional screener) b,d	x	x	x	x	x	x	x	x	x	x	x	
HIV High Exposure Risk Questionnaire +d		X										
Depression/Anxiety (HADS) d			X	X	X	X	X	X	X	X	X	
Functional Impairment (PAOFI) d			X	X	X	X	X	X	X	X	X	
Affect (PANAS) d			X	X	X	X	X	X	X	X	X	
Nicotine Withdrawal (MNWS-R) d			X	X	X	X	X	X	X	X	X	
Smoking Urges (QSU-B) d			X	X	X	X	X	X	X	X	X	
Sleep Quality (PSQI) d			X	X			X					X
Social Support (PIQ) d		X										X
Alternative Reinforcers (PES) d		X										X
Perceived Risks and Benefits of Quitting (PRBQ) d		X										
Subjective Cognitive Complaints d			X	X	X	X	X					X
Impact of COVID-19 on Smoking Survey d		X										X f
TREATMENT MEASURES												
TN Adherence d							X	X	X	X	X	
TN Side Effects (SEC) d						X	X	X	X	X	X	
NEUROCOGNITIVE OUTCOMES												
Executive Function (N-back, Stroop)			X	X								
Verbal Learning & Memory (HVLT)			X	X								
Response Inhibition (Stop task)			X	X								
Delay Discounting Task			X	X								
SMOKING OUTCOMES												
Carbon Monoxide (CO) e		X	X	X	X	X	X	X	X	X	X	
Smoking Rate (TLFB) d			X	X	X	X	X	X	X	X	X	
RHYTHM MONITORING SUB-STUDY ONLY												
Cardiac Supplemental Medical History d		X										
Risk Assessment Battery d		X										
BASIS-24 d		X										
SF-12 d		X										
Quick Inventory of Depression Symptomatology d		X										

Rhythm Monitoring Device Application c					X					X		
RECRUITMENT PILOT OUTCOMES												
% Eligible at Intake			X									
Attitudes Toward Research		X					X					X
Compared Riskiness Scale d	X	X										
Perceived Coercion Scale d			X									
Previous Experience with Research Studies		X										
Prior Persuasion Questions d			X									
Personal Financial Well-Being		X										

*Note. L1 and L2 = laboratory session 1 and 2, respectively; PQ = Pre-Quit visit; TQD = Target Quit Date; EOT = End-of-Treatment; MINI = Mini International Neuropsychiatric Interview; C-SSRS = Columbia Suicide Severity Rating Scale; HVLT = Hopkins Verbal Learning Test*

a HIV-infected group only

b HIV negative group only

c A viral load assessment, conducted as part of routine clinical care any time between Week 4 and Week 12, will be ascertained through medical record review or contact with health clinic and recorded.

d Only administered if a diagnosis of bipolar disorder is self-reported or revealed via MINI at intake

e Rhythm monitoring devices are worn for two weeks. The second device may be mailed to participants for self-application if an in-person visit is not necessary.

f Measures will primarily be completed remotely via phone or videoconference to limit the length of in-person visits (if applicable)

g Weeks 3-12, participants will self-report using the ICO device. If unable to use the device, and abstinence is reported, participants may be asked to come to our center for CO verification.

h Only administered to participants who were enrolled and active on 3/16/2020 and completed their EOT (Week 12) on or after 3/30/2020.

## 2. Statistical Analysis

### **Power Analysis and Sample Size.**

Our study is a longitudinal between-subject design that seeks to test the following hypotheses: 1) that HIV+ smokers experience larger abstinence-induced cognitive deficits than HIV- smokers (Aim 1); 2) have lower quit-rates than HIV-smokers following standard treatment (Aim 2); and 3) that the association between HIV status and relapse is mediated by abstinence-induced cognitive deficits (Aim 3). We have designed our study to achieve 80% power, testing at a global  $\alpha=0.05$  for each of the hypothesis families (Figure 1). Our sample size of 300 was determined primarily by Aim 2. Based on prior work, we expect a ~15% difference in abstinence rates between HIV+ and HIV- smokers (Ferketich et al., 2013; Humfleet et al., 2013; Matthews et al., 2013; Silagy et al., 2004). With 150 HIV+ vs. 150 HIV- smokers, we have 80% power to detect a difference of ~15 percentage points in point-prevalence abstinence (60% vs. 45%, 50% vs. 35%, 40% vs. 25%), using a z-test on log-odds with a type 1 error of 5%. For Aim 1, we will test the HIV status by abstinence condition (24-h abstinence vs. smoking-as-usual) interaction for 5 cognitive measures using a linear regression with one between- and one within-subjects factor. We will correct for 5 tests using  $\alpha=0.01$ . We have 80% power to detect medium effect sizes (Cohen's  $d=0.4$ ). For Aim 3, we will test whether abstinence-induced cognitive deficits predict quit rates and, using SEM, test whether cognitive deficits mediate the effect of HIV status on quitting. The primary aim will be to test the overall fraction of the effect mediated, which will be tested at  $\alpha=0.05$ , which gives 80% power to detect small to medium effects ( $d=0.32$ ). For our exploratory aim, the component individual deficits will be treated as secondary and tested individually as part of an exploratory analysis, also with a 5% type 1 error. To characterize cognitive deficits in HIV+ smokers, 150 subjects will give us an estimate for each measure with a 95% CI that is 0.32 standard deviations wide (Upper – Lower limits). We will estimate the within-subject correlation for these as repeated measures, with a 95% CI that is 0.32 wide (Upper – Lower) if  $r=0$ , 0.24 if  $r=0.5$ , and 0.14 if  $r=0.75$ . Power was calculated using PASS software, NCSS, Kaysville, UT.

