report an interest in quitting smoking, evidence suggests that standard smoking cessation treatments have not been very effective (Pacek and Cioe, 2015). Even with transdermal nicotine (TN) – the most widely used over-the-counter treatment for nicotine dependence (Jong et al., 2005; Pierce and Gilpin, 2002) – only 10-15% of HIV-infected smokers successfully quit smoking (Ferketich et al., 2013; Humfleet et al., 2013; Matthews et al., 2013) compared to 30% in the general population (Silagy et al., 2004). Thus, there is a clear need to identify mechanisms that underlie smoking behavior among HIV-infected individuals to guide development of population-specific smoking cessation treatments to help more HIV-infected individuals quit smoking.

**Health Consequences of Smoking Specific to HIV-Infected Individuals.** Recent epidemiological evidence suggests that HIV-infected smokers lose more life-years due to tobacco use than to HIV infection (Helleberg et al., 2013). Tobacco use increases the risk of developing cardiovascular and pulmonary diseases and cancer and can negate the beneficial effects of HAART among HIV-infected individuals (Feldman et al., 2006; Humfleet et al., 2009). Compared to HIV-infected non-smokers, smokers on HAART are less likely to achieve a viral or immunologic response and have a greater chance of developing a viral or immunologic failure (Feldman et al., 2006; Marshall et al., 2009). The risk of developing non-AIDS-defining cancers, including lung cancer, is two to three-fold higher among HIV-infected individuals compared to the general population (Brugnaro et al., 2015). Moreover, smoking among HIV-infected individuals can exacerbate HIV-related symptoms (e.g., respiratory problems, pulmonary pneumonia), worsen overall quality of life (Crothers et al., 2005; Cui et al., 2010; Turner et al., 2001; Webb et al., 2007), and increase the likelihood of death (Pines et al., 2011). Another consequence of smoking on HIV pathogenesis is that it can accelerate the incidence and progression of HIV-associated neurocognitive disorders (HANDs) (Purohit et al., 2013; Purohit et al., 2011).

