**Aim 1.** We will analyze neurocognitive data with multiple linear regression using a GLM framework. The outcomes will be cognitive deficits measured as a change in response values (see **Section D.4.d.** for description) due to abstinence challenge (24-h abstinence vs. smoking-as-usual). The hypothesized interaction effect of HIV+ status by abstinence condition will be tested by including dichotomous predictors, and examining the corresponding *z*-score. Although the groups will be matched on key variables, we may also include a small number of covariates (e.g., nicotine dependence, Shipley IQ) that show potential to control for error, admitted to the model at  $p=0.1$ . In conjunction with Aim 1, we will be estimating cognitive measures for the HIV+ group, within-subject correlations, and deficits that arise from abstinence challenge. We will summarize point estimates and provide 95% confidence intervals.

**Aim 2.** We will analyze point-prevalence quit rates using logistic regression. The hypothesized effect of HIV status (HIV+ vs. HIV-) will be tested by including a dichotomous term using the *z*-score. A small number of other potential controlling variables will be tested for inclusion ( $p=0.1$ ). Outcomes of the logistic regression analyses will be characterized by odds ratios (e.g., odds of quitting smoking) and 95% confidence intervals. Point-prevalence quit rates at EOT are the primary outcome. Secondarily, we will conduct logistic regression analyses for other assessments of quit rates, including prolonged and continuous abstinence.

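### Aim 2 power: at two of the three listed rate pairs (60 v 45% and 50 v 35%), 150 per group gives about 74% power if the test is two-sided, not the stated 80%, and sidedness is not stated

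*Combined protocol and SAP*

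**What the plan says.** In the combined protocol and SAP, section 2 (Statistical Analysis), the paragraph on power and sample size makes Aim 2 the basis for the trial's size: "Our sample size of 300 was determined primarily by Aim 2". It then states that, with 150 smokers in each group, "we have 80% power to detect a difference of ~15 percentage points in point-prevalence abstinence (60% vs. 45%, 50% vs. 35%, 40% vs. 25" per cent). The test is named, "using a z-test on log-odds with a type 1 error of 5" per cent, but its sidedness is not.

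The Aim 2 paragraph under Data Analysis plans a logistic regression with a z-test on the HIV term. Results are to be given as "odds ratios (e.g., odds of quitting smoking) and 95% confidence intervals". Sidedness is not stated there either. The Aim 2 hypothesis itself is directional: lower abstinence in HIV+ smokers.

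The main-study background cites quit rates with the nicotine patch that lie below all three listed pairs: "only 10-15% of HIV-infected smokers successfully quit smoking", against 30% in the general population.

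**The concern.** The sentence gives every input needed to check it except sidedness: group sizes, rates, test, alpha and claimed power. A 15-point difference is harder to detect near 50%, where binomial variance is greatest, than lower down. One power figure is therefore unlikely to fit all three pairs, and the two pairs nearest 50% are the ones at risk.

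This is the sentence that justifies 300 participants. If true quit rates fell in the 35–60% range of the first two pairs, the type 2 error under a two-sided test would be about 26% rather than 20%, and a null Aim 2 result would be judged against the wrong figure. The Aim 3 mediation analysis is also planned on the assumption that Aim 2 shows a significant effect.

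**Working it through.** **Inputs.** n = 150 per group, the three rate pairs, alpha = 0.05, a z-test on log-odds and a claimed power of 80%, all from the power paragraph. Sidedness is not given, so both readings are shown.

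**Formula.** For rates p1 and p2, with q = 1 − p:

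- L = |ln(p1/q1) − ln(p2/q2)|
- SE = √[1/(n·p1·q1) + 1/(n·p2·q2)]
- Power = Φ(L/SE − z), with z = 1.960 (two-sided 5%) or 1.645 (one-sided 5%)

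**Worked example, 60 v 45%.** L = ln(1.5) − ln(0.8182) = 0.6061. SE = √[(4.1667 + 4.0404)/150] = 0.2339. L/SE = 2.591. Two-sided power = Φ(2.591 − 1.960) = Φ(0.631) = 73.6%. One-sided power = Φ(2.591 − 1.645) = Φ(0.946) = 82.8%.

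| Pair | L | SE | L/SE | Two-sided | One-sided | n per group for 80%, two-sided |
|---|---|---|---|---|---|---|
| 60 v 45% | 0.6061 | 0.2339 | 2.591 | 73.6% | 82.8% | 175.3, so 176 |
| 50 v 35% | 0.6190 | 0.2366 | 2.617 | 74.4% | 83.4% | 171.96, so 172 |
| 40 v 25% | 0.6931 | 0.2517 | 2.754 | 78.6% | 86.6% | 155.2, so 156 |

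The last column is n = (1.960 + 0.842)² × [1/(p1·q1) + 1/(p2·q2)] / L². The stated 80% is reproduced within 2 points only for 40 v 25%, two-sided.

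**Detectable difference.** Holding the higher rate at 60%, 50% or 40% and solving for two-sided power of 80% with 150 per group gives 16.2, 16.0 and 15.2 points.

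**Does the choice of formula matter?** Two-sided 5%, 150 per group:

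| Method | 60 v 45% | 50 v 35% | 40 v 25% |
|---|---|---|---|
| Log-odds z-test (as named) | 73.6% | 74.4% | 78.6% |
| Same test, exact binomial enumeration | 74.5% | 76.0% | 79.6% |
| Proportions, pooled variance | 74.2% | 75.0% | 79.5% |
| Proportions, unpooled variance | 74.9% | 75.8% | 80.2% |
| Proportions, continuity-corrected | 70.3% | 71.1% | 75.8% |

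Without the continuity correction, the first two pairs stay at about 74–76% and the third at about 79–80%. No variant tried, one- or two-sided, brings all three pairs within 2 points of 80%.

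**Which sidedness did the plan use?** The neighbouring main-study power claims can be tested as two-group t-tests with 150 per group. That is an assumption, because neither is described as one.

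- Aim 1 ("We have 80% power to detect medium effect sizes", d = 0.4, alpha = 0.01): 80.8% two-sided, 86.9% one-sided.
- Aim 3 (d = 0.32, alpha = 0.05): 78.9% two-sided, 86.9% one-sided.

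Both stated 80% figures fit two-sided tests. So does the planned 95% confidence interval for the Aim 2 odds ratio, which corresponds to a two-sided 5% test.

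**Background rates.** The same two-sided formula gives about 86% power at 30 v 15% and about 99% at 30 v 10%.

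**The case against.** The strongest reply is that the shortfall rests on a two-sided test, which the plan never specifies, while the hypothesis is directional. At one-sided 5% all three pairs exceed 80%, so the sentence would be true as a minimum. With a continuity correction, one-sided power is 80.3%, 81.0% and 84.6%, which nearly matches the first two pairs. The rhythm-monitoring sub-study also points that way: d = 0.7 with 25 per group and a 5% t-test gives 67.9% two-sided and 78.7% one-sided, against a stated 80%. The Aim 1 and Aim 3 comparisons above are indirect, since those aims concern an interaction and a mediated proportion.

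This stands as a reason to ask for sidedness first. It does not rescue the sentence. The sub-study is a separate calculation, and its other claim (r = 0.4 at alpha 0.01 with 50 participants) fits neither side, at about 63% two-sided and 72% one-sided. The one-sided reading does not give 80% at all three pairs either.

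Three further points limit the consequence:

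- The difference is written as approximate, and the two-sided miss is about one percentage point. That is fair on the difference scale, but at two pairs the plan itself lists, the stated power is still about 6 points too high.
- The background rates give power above 80%. This is correct, but none of the listed pairs uses those rates.
- The analysis set may exceed 300, because 300 is the target for completers and the primary analysis takes everyone who finished the laboratory phase and began treatment. With an illustrative 175 per group, two-sided power would be 79.9%, 80.7% and 84.5%. The plan does not give that number, its power sentence uses 150 per group, and it acknowledges that coding missing data as smoking can shrink group differences.

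**Conclusion.** The concern holds, as a minor point. Assuming a two-sided 5% test with 150 per group, the stated 80% is too high by about 6 points at 60 v 45% and 50 v 35%, and by about 1 point at 40 v 25%. The arithmetic is firm across the uncorrected methods; a continuity correction lowers the figures further. Two-sidedness is an inference from the planned confidence intervals and the Aim 1 and Aim 3 figures, not a statement in the plan. If one-sided 5% was meant there is no shortfall, but power is then 83–87% and the sentence still needs its sidedness and corrected figures. The adequacy of the trial's size at the background quit rates is not in question.

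**What to change.** State in the power paragraph that the Aim 2 test is two-sided. Then replace the single 80% figure with about 74%, 74% and 79% for the three listed pairs, or say that 150 per group gives 80% power for differences of about 16, 16 and 15 points from 60%, 50% and 40%. If a one-sided test was intended, say so in both the power paragraph and the Aim 2 analysis paragraph, and give about 83%, 83% and 87%. Optionally, add the scenario that matches the background evidence: about 86% power at 30 v 15% and about 99% at 30 v 10%, two-sided.

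The cost is text only: a statement of sidedness and corrected power figures. The sample size, design and analysis do not change. For reference, 80% two-sided power at the listed pairs would take 176, 172 and 156 per group.

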### **2. Accrual**

For this trial, we project that we will screen about 1200 smokers over 63 months (allowing six months to complete follow-up). Based on our varenicline trial with HIV-infected smokers (IRB Protocol #815435) and the present inclusion/exclusion criteria, we expect about one-third of these smokers to be eligible for the trial (n = approximately 415). To be conservative, given the possible health problems evident in this population of smokers, we will project less than 25% of participants will withdraw from the trial and more than 75% of subjects will complete follow-ups to have 300 complete the study. As is advised in smoking cessation trials (Hughes et al., 2003), intent-to-treat will be used for primary analyses, with missing outcome data coded as smokers.

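### Aim 1's flat alpha of 0.01 for five tests is valid, but Holm's step-down procedure would keep the same 5% family-wise bound with equal or greater power for one changed sentence

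*Combined protocol and SAP*

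**What the plan says.** The multiplicity rule for Aim 1 stands in one place, Power Analysis and Sample Size, under Statistical Analysis. That section sets a global alpha of 0.05 for each family of hypotheses. It describes Aim 1 as the HIV-status-by-abstinence-condition "interaction for 5 cognitive measures using a linear regression with one between- and one within-subjects factor", and then states "We will correct for 5 tests using" alpha = 0.01. It claims 80% power at Cohen's d = 0.4. The group sizes come from the Aim 2 sentence, "With 150 HIV+ vs. 150 HIV- smokers, we have 80% power". The Accrual section allows for dropout separately: "more than 75% of subjects will complete follow-ups to have 300 complete the study".

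The Aim 1 paragraph under Data Analysis defines the outcome scale ("The outcomes will be cognitive deficits measured as a change in response values") and promises 95% confidence intervals, but adds no multiplicity rule. No step-down or other sequential procedure is named anywhere in the document. The word Bonferroni is not used either, but 0.05/5 = 0.01 is that method.

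**The concern.** Under a flat threshold each of the five interactions must reach p ≤ 0.01 whatever the other four show. Once one null hypothesis has been rejected, only four can still be falsely rejected, so testing the rest at 0.05/5 is stricter than the 5% bound requires. Holm's procedure uses that slack.

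At stake is the number of domain-level deficits that Aim 1 can declare. The Aim 1 hypothesis under Objectives names both verbal and working memory, so a second declaration is of interest, and the second and later rejections are where a step-down rule helps.

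**Working it through.** **Inputs.** From Power Analysis and Sample Size: 150 per group, d = 0.4, five tests, per-test alpha 0.01, family alpha 0.05. Assumptions: d is on the SD of the abstinence-minus-smoking change score; tests are two-sided (not stated for Aim 1); the correlation between measures, which the documents do not give, is 0, 0.3 or 0.5. No further dropout is applied, because the 300 are completers.

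**The plan's own figure.**
- Noncentrality: 0.4 × √(150/2) = 0.4 × 8.660 = 3.464.
- Two-sided critical value at 0.01: 2.576.
- Normal power: Φ(3.464 − 2.576) = Φ(0.888) = 81.3%. With the noncentral t on 298 degrees of freedom it is 80.8%.

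The stated 80% therefore reproduces. A one-sided test would give 87%, which does not match, so two-sided is the natural reading.

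**Error control of the flat rule.** The bound is 5 × 0.01 = 0.05. Under independence the error is 1 − 0.99⁵ = 4.9%.

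**Holm's rule.** Order the p-values, compare the j-th smallest with 0.05/(6 − j), and stop at the first failure. The thresholds are 0.0100, 0.0125, 0.0167, 0.0250 and 0.0500.
- *It never rejects fewer.* Every threshold is at least 0.01, so any p-value that passes the flat rule passes here.
- *The bound is the same.* With m true nulls, the first false rejection must come at or before step 6 − m, where the threshold is at most 0.05/m. Summed over m nulls this is at most 0.05, under any correlation.
- *The chance of at least one rejection is the same.* Both rules begin by asking whether the smallest p-value is at most 0.01.

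**Size of the gain at d = 0.4.** Simulation of five z-statistics, 400,000 replicates per scenario; ranges run over correlations 0 to 0.5.

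| Measures truly affected | Power per affected measure, flat 0.01 | Same, Holm | Power to show all affected, flat 0.01 | Same, Holm |
|---|---|---|---|---|
| 1 | 81% | 81% (+0.1 point) | 81% | 81% |
| 2 | 81% | 83% | 66–70% | 70–73% |
| 3 | 81% | 84–85% | 54–63% | 63–70% |
| 5 | 81% | 89–91% | 35–54% | 69–77% |

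At d = 0.3 with all five affected, power per measure goes from 51% to 60–61%.

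**Error under Holm.** Simulated family-wise error was 0.032 to 0.049 in every scenario that contained a true null, so never above 0.05. With three true effects at d = 0.4 it was about 0.04, against about 0.02 for the flat rule.

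**The case against.** The strongest reply is that nothing is wrong. The plan promises a 5% family-wise bound and 80% power at d = 0.4, and it delivers both. That stands: this is an efficiency point only.

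Three stronger readings are tempting, and the documents do not support them.

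- *That the expected gain is 8 to 10 points per measure.* That needs all five effects to be real at d = 0.4. The Aim 1 hypothesis names verbal and working memory, and the Background and the Exploratory Aim treat domain-specific effects as open. Two affected measures is the nearest scenario, with a gain of about 1.5 points. If each memory domain supplied two of the five scores, the gain would lie between the three-effect and five-effect rows, but the plan does not say so.
- *That Aim 1 is more likely to succeed under Holm.* The aim asks whether deficits are greater, and the plan does not say how many measures must be significant. If one is enough, the gain is nil.
- *That undeclared Aim 1 effects would be lost as mediators in Aim 3.* The Aim 3 analysis enters all the candidate mediators together and tests global mediation at its own alpha of 0.05. Its only stated condition is an HIV effect on abstinence at end of treatment. Aim 1 significance selects nothing there.

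Two practical cautions also stand. Holm uses more of the 5% allowance and has no simple matching simultaneous intervals; this matters little here, since the Aim 1 analysis promises only ordinary 95% intervals. And Holm, like the flat rule, needs a fixed list. The Neurocognitive Outcomes section describes five tasks but labels seven outcomes primary. With seven tests, the flat 0.01 would bound the error at 7 × 0.01 = 7%, and Holm would have to start at 0.05/7 = 0.0071. Naming the five measures matters more than the choice of procedure.

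**Conclusion.** The point holds as a free improvement, not as an error. Under the stated two-domain hypothesis, read as two affected measures, Holm raises power per measure from 81% to 83%, and power to show both from 66–70% to 70–73%. The range runs from about 0.1 point with one real effect to 8–10 points if all five are real. The 5% bound needs no assumption about correlation; the power figures rest on two-sided tests, equal effects of d = 0.4 on the change-score SD, 150 per group, and correlations of 0 to 0.5. A reader should not infer that the current correction is invalid, that the 80% figure is wrong, or that Aim 3 would change.

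**What to change.** Before any Aim 1 data are analysed, replace the correction sentence in Power Analysis and Sample Size by: *The five interaction tests will be corrected by Holm's step-down procedure at family-wise alpha 0.05.* Repeat the rule in the Aim 1 paragraph under Data Analysis, with the five measures listed by name, one score each. Keep 80% power at d = 0.4, described as a lower bound per measure.

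The cost is this edit and the fixed list, which the current rule needs as well. No extra participants are required. If simultaneous intervals are wanted, keep them at the 99% level (1 − 0.05/5) and note that a measure declared significant at a later Holm step may have a 99% interval that includes zero.
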